### Summary of the study proposed:

The proposed study will examine the use and effectiveness of a novel strength training device – The S-Press within an NHS environment. The S-Press is a portable exercise device that can be used seated or lying down and specifically targets the knee extensors and flexors. The knee extensors are particularly important in the performance of activities of daily living such as rising from a chair, walking up and down stairs and walking.

Resistance training is the most effective strategy to help to reduce muscle wasting in response to ageing or chronic disuse; however as current in-patient settings likely fail to produce an overload stimulus to the muscle for hypertrophy and strength gains, there is a need to develop new interventions and equipment to help deliver this. The S-Press is designed by a Physiotherapist with the goal of increasing muscle strength and improving physical function in patients who may be confined to their bed or chair or unable to join in with standard physiotherapy treatments.

This mixed methods study will examine the efficacy of the S-Press to improve muscle size using B-Mode Ultrasound and physical function, using sit to stand x5 with use over 6 weeks, alongside the qualitative experience of the use of the S-Press through a one to one semi structured interview. Data collected will enable CE marking of the device along with the existing data collected and enable onward NHS studies.

This novel device should improve outcomes for users, with the eventual aim of easing pressure on NHS staff and produce NHS cost savings by helping prevent delays in discharge which cost the NHS £820 million each year.

#### **Background and scientific justification:**

Prevention of hospital associated deconditioning is an immediate healthcare unmet need. 10.5 million vulnerable older adults are admitted into UK hospitals annually. Muscle deconditioning begins within 2 days, with baseline strength reducing by up to 20% in 1 week and 68% of patients discharged below their pre-admission level of function (Kortebein et al., 2008; Falvey et al., 2015). These patients are 3x more likely to be re-admitted within 30 days and de-conditioning is responsible for 47% of delayed discharges (Lim et al., 2006).

Preserving muscle strength and function has many contributing factors; with physiotherapy having a key role. Progressive resistance exercise (PRE) is known to increase muscle strength in even the

Short title: S-Press

Sponsor code: JT Rehab-01

IRAS number: 251647

frailest individuals (Suetta et al., 2007) and researchers suggest that PRE should be used more in hospitals to prevent deconditioning and improve outcomes (Falvey et al., 2015). There is limited PRE equipment available for physiotherapists, its use compounded by a lack of clinical time and staff. The new S-Press portable leg strengthening device has been designed by a physiotherapist to improve access to effective PRE for vulnerable older patients and ease workload for physiotherapists.

PRE benefits have been well documented since the 1950s, yet physiotherapists working in hospitals rarely use it with patients. There are many reasons for this including health barriers, institutional barriers, changing demand on physios within the NHS and lack of appropriate equipment for effective use. Guthrie Smith (1943) invented the revolutionary sling/spring suspension format used for decades by physiotherapists. The S-Press utilises this tried and tested principle in a re-imagined /re-designed mechanical gym-equipment style, for portability, accessibility and use by vulnerable temporarily immobile patients in need of muscle strengthening if confined to their bed or chair.

Leg muscle weakness, especially knee-extensor strength, is associated with increased falls risk (Tinetti 1988; Wolfson 1995) and decrease in function (Van Roie et al., 2011). Leg strength gain is associated with improvements in sit to stand, gait, transfers, stair climbing and confidence (Chandler 1998). A study is needed to assess if providing PRE to older adults via use of the S-Press device has a beneficial effect on muscle strength and if this translates into functional task improvement.

PPI using expert patients and clinicians from three NHS Trusts have participated in focus groups. A national proof of market study run by NIHR Devices for Dignity has shown a positive response to the S-Press concept and recognition of its potential value. These discussions have all contributed to the final S-Press design decisions and features. In-patient feedback on physiotherapy interventions describes a feeling of achievement and a sense of doing 'real physio' when using exercise devices, as compared to 'just walking'. Competition between patients is also known to be beneficial and encourages participation and improvement; all achievable with S-Press use.

Success criteria will be to show clinically significant improvements in lower limb muscle size, sit to stand ability of 15 - 20 older adults, and the views on use and acceptability with users and staff, following 6 weeks of training with the S-Press. Evidence that this improvement in lower limb muscle size and strength transfers to an improvement in a range of selected validated functional skills and sufficient user qualitative feedback will allow CE marking of the device enabling further NHS studies.

The project lead and S-Press inventor is a physiotherapist with 22 years of older people's rehabilitation experience. Researchers from Sheffield Hallam University will devise, run, and analyse the quantitative data from the study. The qualitative element of the real-world evaluation will be

Short title: S-Press

Sponsor code: JT Rehab-01

IRAS number: 251647

performed and analysed by the research team at Northamptonshire Healthcare NHS Trust. Devices for Dignity have previously provided proof of market evidence and will provide regulations assistance, health economics and commercialisation to enable CE marking. S-Press development has been funded by Versus Arthritis.

To gain CE mark as a class 1 medical device a clinical evaluation needs to be performed with older people. NHS patients will be perfect participants to trial this fully safety tested exercise device.

### **Description of intended purpose and mode of action of device:**

The S-Press is a mechanical single leg strengthening device, using spring resistance to provide a progressive increase in resistance level from 3kg to 20kg resistance level. The S-Press requires physical effort from the user to work, through a push or pull action of the leg whilst the leg is positioned on a supportive leg rest. The S-Press can be used on the bed or positioned on the floor if user is sitting in a chair. The intended purpose of the S-Press is to strengthen the quadriceps and hamstring muscles and provide improvement in the physical ability of the user, such as sit to stand, transfer and walking ability.

### **Research aims:**

To assess the efficacy, feasibility, usability, and acceptability of use of the *S-Press* by NHS staff using it with an older NHS in-patient population, for strengthening quadriceps and hamstring muscles and improving physical impairment.

#### **Research objectives:**

### **Primary Objectives:**

The primary objectives are to quantify changes in the following in response to 12 sessions (2x per week for 6 weeks) of using the S-Press device supervised by a Physiotherapist. The primary outcomes are to assess:

- Functional improvements using the 5x sit to stand test.
- Morphological changes, measuring muscle thickness of the Vastus Lateralis and Rectus Femoris muscle using B-Mode ultrasound.
- Any safety issues with *S-Press* use with older users.
- Perceptions of usability of the S-Press with older adult users and care givers.

Short title: S-Press

Sponsor code: JT Rehab-01

IRAS number: 251647

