#### Type of study design:

This is a single-arm, mixed methods study design. Quantitative and Qualitative research methods planned.

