#### Study classification:

Efficacy and feasibility study.

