### Sample size justification:

For the study we will aim to recruit 15 - 20 NHS in-patient participants across the 4 sites. Sample size aligns with previous research studies using similar methodology (e.g., Dibble et al. 2006; Alkner, et al., 2004; Frontera, et al., 1988; Fiatarone, et al., 1990; Grimby, et al., 1985; Pyka, et al. 1994; Hagerman et al. 2000; Hepple, et al. 1997)

Typical exercise training studies of this length have 10-15 participants per arm of the trial. This would conventionally include a control group. As this is a feasibility trial, the advice from our RDS was that a control group was not required. An N of 12 has been recommended as a minimum number of participants per group to be recruited for a clinical trial where there is no prior information to guide sample size (Julious 2005). This figure is suggested to represent the lower threshold required to estimate the standard deviation of measures with adequate precision. We aim to recruit 15-20 participants to the study to allow for a predicted 20% attrition rate.

This low number of patient participants per site will provide a low burden for the staff participants.

Short title: S-Press

Sponsor code: JT Rehab-01

IRAS number: 251647

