#### **Exercise Sessions**

First, participants will be asked to warm up supervised by the physiotherapist, this will incorporate some low intensity range of movement exercise and light stretching.

Staff participants will set up the patient participant using the S-Press protocol for set up. Patients can remain on the bed or in the chair so will not require transferring or position change by the staff for use.

Short title: S-Press

Sponsor code: JT Rehab-01

IRAS number: 251647

Initial assessment of appropriate resistance level will be examined at the beginning of the first session, by assessing the patient participants 1 repetition max (1RM) level (maximum resistance level ability - Instructions stated in set up protocol).

Participants will then complete 3 sets of 10 repetitions on each leg firstly for the knee extensors and then the knee flexors. The S-Press allows both Concentric and Eccentric muscle actions, so muscle groups are performed independently. A guide of 1 minute's rest will be provided in between sets and legs, although more rest will be allowed if required by the participants. The amount of time per exercise session will be approximately 30 minutes.

Blood pressure and heart rate will be measured before the exercise session begins, mi-way through and again at the end of the session. This is to ensure that there is maintenance of optimal levels of blood pressure and heart rate and monitoring of any adverse effects. These measurements are regularly taken by therapy staff to assess their patients' conditions before and during physical intervention.

Data from the assessments will be analysed using paired t-tests. As this trial is an efficacy and feasibility trial descriptive statistics (mean, standard deviation and % Change) will be calculated. In addition, Cohen's D will be used to determine effect sizes to quantify the magnitude of any differences in variables. A p value of p<0.05 will be used to determine significance, with effect size of <0.2=small; 0.5= moderate; >0.8 large.

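### An uncontrolled before-after change is worded as a response to S-Press, and the Cohen's d bands are wrong as written

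*Protocol*

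**What the plan says.** **Design and label.** Under Type of study design: "This is a single-arm, mixed methods study design". Under Study classification: "Efficacy and feasibility study". The Summary, Research aims and Purpose of the study also speak of efficacy, and the Summary and Purpose link the data to CE marking.

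**Objective.** The section headed Primary Objectives sets this task: "quantify changes in the following in response to 12 sessions (2x per week for 6 weeks) of using the S-Press device", with 5x sit to stand and muscle thickness as the quantitative measures.

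**Control.** Sample size justification says of comparable training studies: "This would conventionally include a control group". It then continues: "As this is a feasibility trial, the advice from our RDS was that a control group was not required". The section on the post-market plan calls the study preliminary.

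**Other therapy.** The justification for NHS staff involvement says that patients have daily ward therapy, which includes strengthening, from a team whose role is to restore sit to stand. The staff inclusion criteria place S-Press inside the normal 30-minute session.

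**Analysis.** The last paragraph of Exercise Sessions states: "Data from the assessments will be analysed using paired t-tests". It goes on: "As this trial is an efficacy and feasibility trial descriptive statistics" will be calculated (mean, SD and % change), together with Cohen's d. It ends: "A p value of p<0.05 will be used to determine significance, with effect size of <0.2=small; 0.5= moderate; >0.8 large".

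**Success.** Background and scientific justification makes *clinically significant* improvement in muscle size and sit to stand the success criterion. The Protocol gives no size for either.

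**The concern.** The paired t-test asks whether the mean total change is zero. The objective asks what change S-Press produced. The two coincide only if nothing else moves the outcome over 6 weeks. Here the patients are in hospital for therapy, and one primary outcome is the task which that therapy aims to restore.

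The reason given for having no control rests on the study being a feasibility trial, while the analysis paragraph and the classification call it efficacy as well. Feasibility, usability and safety can be studied in one arm. A statement that the device caused the change cannot rest on the same reason.

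At stake is how the result is read in data meant to support CE marking. Recovery under ward therapy could be credited to the device; equally, deconditioning could mask a real benefit.

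The bands are a smaller and separate fault: a stated rule that gives no effect a positive-sounding label and gives most mid-sized effects no label. An undefined *clinically significant* leaves the success criterion open to judgement after the results are known.

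**Working it through.** **1. The plan's own figure.** Sample size justification starts from a minimum of 12 and 20% attrition: 12 / (1 − 0.20) = 15, the lower end of the target of 15–20. This reproduces. The Protocol states no power, target effect or SD, so there is no power figure to check. Numbers analysed: 15 × 0.8 = 12; 20 × 0.8 = 16; 20 with no loss.

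**2. What the test estimates.** For each patient, observed change = device effect + change from ward therapy + recovery − deconditioning + error. The paired t-test addresses the mean of the sum. With one arm, no term can be estimated alone.

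**3. Illustration of the consequence.** Assumptions, none of them from the Protocol: the device effect is zero; background change has standardised size dz (mean change / SD of change, positive = favourable); the test is two-sided at 0.05; one outcome is considered. Then

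P(significant improvement) = P(T > t₀.₉₇₅,ₙ₋₁), with T noncentral t on n − 1 df and noncentrality dz·√n.

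Critical values are 2.201, 2.131 and 2.093 for n = 12, 16 and 20.

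| Background dz | n = 12 | n = 16 | n = 20 |
|---|---|---|---|
| −0.2 | 0.47% | 0.33% | 0.25% |
| 0 | 2.5% | 2.5% | 2.5% |
| 0.2 | 9% | 11% | 13% |
| 0.5 | 35% | 46% | 56% |

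Only the row with zero background change gives the nominal 2.5%.

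**4. Bands, read literally.**

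| Value of d | Label in the Protocol |
|---|---|
| 0 | small |
| any value below 0.2 | small |
| 0.2 up to 0.5 | none |
| exactly 0.5 | moderate |
| above 0.5 up to 0.8 | none |
| above 0.8 | large |

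The fault is visible without calculation. How it meets the significance test depends on the SD used for d, which the Protocol does not name:

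- SD of change: smallest significant |d| = t₀.₉₇₅,ₙ₋₁ / √n = 2.201/√12 = 0.64, 2.131/√16 = 0.53, 2.093/√20 = 0.47. All are unlabelled.
- Baseline or pooled SD with pre-post correlation r (equal SDs assumed): multiply by √(2(1 − r)). At r = 0.90 this gives 0.28, 0.24 and 0.21, still unlabelled. At r = 0.95 it gives 0.20, 0.17 and 0.15, so the smallest significant result is at the 0.2 boundary for n = 12 and in the band called small for n = 16 and 20.

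**The case against.** **The design is disclosed.** The Protocol declares a single arm, says that a control would be conventional, cites advice for leaving it out, and calls the work preliminary and a step to further studies. This stands. Neither the design nor the paired t-test is at fault, and one limitation statement is enough; disclaimers in every section that mentions efficacy would be excessive. What remains is that no section says the change cannot be attributed to the device, and the primary objective says the opposite.

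**Background change may not be favourable.** The Background cites strength losses of up to 20% within a week and 68% of patients leaving below their earlier level of function. The Summary doubts that in-patient settings overload muscle enough for growth. On the other side, participants are medically stable and admitted for therapy, so recovery is also plausible. A reader might infer that a positive result would necessarily overstate S-Press. The documents do not support that: the bias has no known sign. This limits the claim but leaves the attribution problem in both directions.

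**Session counts are not exposure.** A reader might count 12 S-Press sessions against daily therapy and conclude that most of the strength stimulus comes from elsewhere. The daily work mixes strengthening and mobility, and the Protocol says that strengthening is limited in many Trusts by equipment. The count does not measure the competing stimulus.

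**Other protections exist.** Familiarisation, the 48–72 hour gap before post-testing and blinded image reading reduce learning effects, transient fluid change and reader bias. They do not address concurrent therapy.

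**The bands are probably shorthand** for 0.2, 0.5 and 0.8. That is likely, and mean, SD and % change are reported too, so little hangs on the label. The rule as written is still wrong.

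**Conclusion.** The point holds in this form: the plan measures total before-after change and words it as a response to S-Press and as efficacy, while the reason given for having no control covers feasibility only. This should be corrected; it does not prevent the study from running.

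Its size cannot be stated from the documents. On the assumed range of background dz from −0.2 to 0.5, the chance that an inert device shows a significant improvement on one outcome runs from 0.2–0.5% to 35–56% with 12 to 20 patients. These figures show how far the result depends on an unknown; they do not predict it.

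The band error is certain from the text and minor in effect. It would go too far to say that a just-significant result always falls in the unlabelled range: that is true if d uses the SD of change, but not for a baseline or pooled SD with a pre-post correlation of 0.95.

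On *clinically significant*, only the undefined term is a Protocol matter. A reader might also object that the thickness summary (two muscles, two legs) and the handling of patients over 60 s are not fixed. A SAP commonly settles both, and it is not at hand.

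**What to change.** 1. **Primary Objectives.** Replace the wording from *in response to* through to the device name with: *over 6 weeks of ward therapy that includes 12 S-Press sessions (2x per week)*. Beside the analysis paragraph in Exercise Sessions, add one statement that the quantitative results are uncontrolled before-after changes, are not attributable to the device alone, and are preliminary. Keep the paired t-test and report the mean change with its 95% CI.
2. **Exercise Sessions, bands.** Use |d| < 0.2 negligible, 0.2 to < 0.5 small, 0.5 to < 0.8 moderate, ≥ 0.8 large. Report the direction, and name the SD used for d.
3. **Background, success criterion (minor).** Drop *clinically significant* for any outcome without a sourced threshold set before data are seen.

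Cost: wording and a confidence interval. No control group, extra patients or extra measurements are needed. The price is a more modest efficacy claim.

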#### **Secondary Objective:**

- To meet CE marking requirement
- To enable further follow-on evaluation in different NHS environments
- Commercialisation.

#### Type of study design:

This is a single-arm, mixed methods study design. Quantitative and Qualitative research methods planned.

### Purpose of the study:

To gain user data for feasibility of use and acceptability in the NHS environment and safety and efficacy to enable CE marking for further follow-on NHS studies.

#### Study classification:

Efficacy and feasibility study.

### Sample size justification:

For the study we will aim to recruit 15 - 20 NHS in-patient participants across the 4 sites. Sample size aligns with previous research studies using similar methodology (e.g., Dibble et al. 2006; Alkner, et al., 2004; Frontera, et al., 1988; Fiatarone, et al., 1990; Grimby, et al., 1985; Pyka, et al. 1994; Hagerman et al. 2000; Hepple, et al. 1997)

Typical exercise training studies of this length have 10-15 participants per arm of the trial. This would conventionally include a control group. As this is a feasibility trial, the advice from our RDS was that a control group was not required. An N of 12 has been recommended as a minimum number of participants per group to be recruited for a clinical trial where there is no prior information to guide sample size (Julious 2005). This figure is suggested to represent the lower threshold required to estimate the standard deviation of measures with adequate precision. We aim to recruit 15-20 participants to the study to allow for a predicted 20% attrition rate.

This low number of patient participants per site will provide a low burden for the staff participants.

Short title: S-Press

Sponsor code: JT Rehab-01

IRAS number: 251647

#### Number of centres justification:

Four NHS sites have requested to participate, this will ensure enough participants are able to be recruited who are able to provide informed written consent to be included and maintain a low burden for the participating ward staff.

### Justification for NHS staff involvement and numbers:

The role of the NHS physio team is to enable the fastest recovery of sit to stand and transfer ability to enable speedy discharge of in-patient's home to a familiar environment. Strengthening exercise provision is a standard treatment provided for this purpose, limited in many Trusts by availability of appropriate equipment. Provision of several free exercise devices per site that can deliver effective, specific, sit to stand muscle strengthening for the length of the trial, is a good benefit to the staff and the patients. The number of patient participants is being kept at a low level of 4 patients per site. Senior management have buy-in from the staff and have appropriate safe staffing levels available to participate in the study. Number of exercise sessions will be twice a week to follow national recommendations for strength training, for approximately 30 minutes. Patients are seen daily on the ward for therapy intervention including strengthening and mobility work. Daily, 30-minute sessions are the gold standard for daily therapy interventions.

No specific number of staff participants has been set to be recruited, so there is no added pressure for participation. There will be 2 devices per site available so a minimum of 2 staff members per site is preferred for the study to maximise the benefit and use of the S-Press and for feedback.

